8.1.4 Corticosteroids

Corticosteroids will be used as premedication and prevention of heterologous serum side effects, as well as immunosuppressive agents. Corticosteroids will be administered as Methylprednisolone at the dose of 1 mg/kg (or Betamethasone at equivalent dose), intravenously or orally, from day 1 to 4. Corticosteroids may be increased up to 2 mg/kg, if clinically needed. After day 4, corticosteroids will be continued at least until day 7 and then tapered off within 2-3 weeks post treatment, by a half-dose reduction every 2-4 days.

8.2 Dose Rationale

Eltrombopag has proven beneficial for the treatment of refractory AA, at the dose of 150 mg per day, orally. [28]

8.3 Side Effects

Main side effects of eltrombopag, ATGAM and Cyclosporine A are described below. However, we strongly encourage physicians to refer to the investigator brochures (appendix 4).

8.3.1 Adverse events seen during eltrombopag use

Some adverse events have been previously reported during the use of eltrombopag; they are summarized below.

Risk of hepatotoxicity

Eltrombopag administration can cause abnormal liver function. In clinical studies with eltrombopag, increases in serum alanine aminotransferase (ALT), aspartate aminotransferase (AST) and bilirubin were observed.

These findings were mostly mild (Grade 1-2), reversible and not accompanied by clinically significant symptoms that would indicate an impaired liver function. Across the 3 placebo-controlled studies, 1 patient in the placebo group and 1 patient in the eltrombopag group experienced a Grade 4 liver test abnormality.

Serum ALT, AST and bilirubin should be measured prior to initiation of eltrombopag, every 2 weeks during the dose adjustment phase and monthly following establishment of a stable dose. Abnormal serum liver tests should be evaluated with repeat testing within 3 to 5 days. If the abnormalities are confirmed, serum liver tests should be monitored until the abnormalities resolve, stabilise, or return to baseline levels. Eltrombopag should be discontinued if ALT levels increase (≥ 3 x the upper limit of normal [ULN]) and are:

- progressive, or
- persistent for ≥ 4 weeks, or
- accompanied by increased direct bilirubin, or
- accompanied by clinical symptoms of liver injury or evidence for hepatic decompensation

Exercise caution when administering eltrombopag to patients with hepatic disease (see section on eltrombopag administration)

Thrombotic/Thromboembolic complications

Platelet counts above the normal range present a theoretical risk of thrombotic/thromboembolic complications. In eltrombopag clinical trials in ITP thromboembolic events were observed at low and normal platelet counts. Caution should be used when administering eltrombopag to patients with known risk factors for thromboembolism including but not limited to inherited (e.g. Factor V Leiden) or acquired risk factors (e.g. ATIII deficiency, antiphospholipid syndrome), advanced age, patients with prolonged periods of immobilisation, malignancies, contraceptives and hormone replacement therapy, surgery/trauma, obesity and smoking. Platelet counts should be closely monitored and consideration given to reducing the dose or discontinuing eltrombopag treatment if the platelet count exceeds the target levels. The risk-benefit balance should be considered in patients at risk of thromboembolic events (TEEs) of any aetiology; in these patients, prophylaxis of thromboembolic events is allowed at judge of the investigator, with the agents that he will find more appropriate.

The risk of TEEs has been found to be increased in patients with chronic liver disease (CLD) treated with 75 mg eltrombopag once daily for two weeks in preparation for invasive procedures.

The influence of hepatic impairment on the pharmacokinetics of eltrombopag following repeat administration was evaluated using a population pharmacokinetic analysis in 28 healthy adults and 79 patients with chronic liver disease (37 mild hepatic impairment, 40 with moderate hepatic impairment, and 2 with severe hepatic impairment). Based on estimates from the population pharmacokinetic analysis, patients with hepatic impairment had higher plasma eltrombopag AUC(0- τ) values as compared to healthy volunteers, and AUC(0- τ) increased with increasing Child-Pugh score. Compared to healthy volunteers, patients with mild hepatic impairment had approximately 87 % to 110 % higher plasma eltrombopag AUC(0- τ) values and patients with moderate hepatic impairment had approximately 141 % to 240 % higher plasma eltrombopag AUC(0- τ) values.

Eltrombopag should not be used in ITP patients with hepatic impairment (Child-Pugh score ≥ 5) unless the expected benefit outweighs the identified risk of portal venous thrombosis (see section on eltrombopag administration).

Bleeding following discontinuation of eltrombopag

Thrombocytopenia is likely to reoccur upon discontinuation of treatment with eltrombopag, at least in ITP patients. Following discontinuation of eltrombopag, platelet counts may return to baseline levels within 2 weeks in the majority of ITP patients, which increase the bleeding risk and in some cases may lead to bleeding. This risk is increased if eltrombopag treatment is discontinued in the presence of anticoagulants or anti-platelet agents. In this study for AA, eltrombopag will be discontinued per protocol as described above; if treatment with eltrombopag is discontinued, treatment with eltrombopag may be restarted within the protocol as described above. Additional medical management for bleeding may include cessation of anticoagulant and/or anti-platelet therapy, reversal of anticoagulation, or platelet support. Platelet counts should be monitored weekly for 4 weeks following discontinuation of eltrombopag.

Bone marrow reticulin formation and risk of bone marrow fibrosis

Eltrombopag may increase the risk for development or progression of reticulin fibers within the bone marrow. The relevance of this finding, as with other TPO-R agonists, has not been established yet.

Prior to initiation of eltrombopag, the peripheral blood smear should be examined closely to establish a baseline level of cellular morphologic abnormalities. Following identification of a stable dose of eltrombopag, complete blood count (CBC) with white blood cell count (WBC) differential should be performed monthly. If immature or dysplastic cells are observed, peripheral blood smears should be examined for new or worsening morphological abnormalities (e.g., teardrop and nucleated red blood cells, immature white blood cells) or cytopenia(s). If the patient develops new or worsening morphological abnormalities or cytopenia(s), treatment with eltrombopag should be discontinued and a bone marrow biopsy considered, including staining for fibrosis.

Malignancies and progression of malignancies

TPO-R agonists are growth factors that lead to thrombopoietic progenitor cell expansion, differentiation and platelet production. The TPO-R is predominantly expressed on the surface of cells of the myeloid lineage. For TPO-R agonists there is a concern that they may stimulate the progression of existing haematopoietic malignancies such as MDS.

Cataracts

Cataracts were observed in toxicology studies of eltrombopag in rodents. The clinical relevance of this finding is unknown. Routine monitoring of patients for cataracts is recommended.

Loss of response to eltrombopag

A loss of response or failure to maintain a platelet response with eltrombopag treatment within the recommended dosing range should prompt a search for causative factors, including an increased bone marrow reticulatin.

8.3.2 Adverse events seen during ATGAM use

During > 5 years of post approval marketing experience, the frequency of adverse reactions in voluntarily reported cases is as follows: fever 51%; chills 16%; thrombocytopenia 30%; leukopenia 14%; rashes 27%; systemic infection 13%. Events reported in 5% to 10% of reported cases include abnormal renal function tests; serum sickness-like symptoms; dyspnea/apnea; arthralgia; chest, back, or flank pain; diarrhea and nausea and/or vomiting. Events reported with a frequency of less than 5% include: hypertension, Herpes Simplex infection, pain, swelling or redness at infusion site, eosinophilia, headache, myalgias, or leg pains, hypotension, anaphylaxis, tachycardia, edema, localized infection, malaise, seizures, GI bleeding or perforation, deep vein thrombosis, sore mouth/throat, hyperglycemia, acute renal failure, abnormal liver function tests, confusion or disorientation, cough, neutropenia or granulocytopenia, anemia, thrombophlebitis, dizziness, epigastric or stomach pain, lymphadenopathy, pulmonary edema or congestive heart failure, abdominal pain, nosebleed, vasculitis, aplasia or pancytopenia, abnormal involuntary movement or tremor, rigidity, sweating, laryngospasm/edema, hemolysis or hemolytic anemia, viral hepatitis, faintness, enlarged or ruptured kidney, paresthesias, and renal artery thrombosis.

The recommended management for some of the adverse reactions that could occur with treatment with ATGAM follows:

Anaphylaxis and allergic reactions

Anaphylaxis is uncommon, but may occur at any time during therapy with ATGAM. More frequently, allergic reaction include skin rash, fever and chills. Prophylactic administration of corticosteroids and/or anti-histamine may decrease the frequency of this reaction.

Hemolysis

Can usually be detected only in the laboratory. Clinically significant hemolysis has been reported rarely. Appropriate treatment of hemolysis may include transfusion of erythrocytes; if necessary, administer intravenous mannitol, furosemide, sodium bicarbonate, and fluids. Severe and unremitting hemolysis may require discontinuation of therapy with ATGAM.

Respiratory distress

May indicate an anaphylactoid reaction. Discontinue infusion of ATGAM. If distress persists, administer an antihistamine, epinephrine, corticosteroids, or some combination of the three.

Pain in chest, flank, or back

May indicate anaphylaxis or hemolysis. Treatment is that indicated above for those conditions.

Hypotension

May indicate anaphylaxis. Stop infusion of ATGAM and stabilize blood pressure with pressors if necessary.

Chills and fever

Occur frequently in patients receiving ATGAM. ATGAM may release endogenous leukocyte pyrogens. Prophylactic and/or therapeutic administration of antihistamines, antipyretics, or corticosteroids generally controls this reaction.

Chemical phlebitis

Can be caused by infusion of ATGAM through peripheral veins. This can often be avoided by administering the infusion solution into a high-flow vein. A subcutaneous arterialized vein produced by a Brescia fistula is also a useful administration site.

Itching and erythema

Probably result from the effect of ATGAM on blood elements. Antihistamines generally control the symptoms.

Serum-sickness like symptoms

In aplastic anemia patients have been treated with oral or IV corticosteroids. Resolution of symptoms has generally been prompt and long-term sequelae have not been observed. Prophylactic administration of corticosteroids may decrease the frequency of this reaction.

Hepatic and Renal Function tests

In patients with aplastic anemia and other hematologic abnormalities who have received ATGAM, abnormal tests of liver function (SGOT, SGPT, alkaline phosphatase) and renal function (serum creatinine) have been observed.

8.3.3 Adverse events seen during Cyclosporine A use***Hypertension***

Hypertension, which is usually mild to moderate, may occur in approximately 50% of patients following renal transplantation and in most cardiac transplant patients.

Glomerular Capillary Thrombosis

Glomerular capillary thrombosis has been found in patients treated with cyclosporine A and may progress to graft failure. The pathologic changes resemble those seen in the hemolytic-uremic syndrome and include thrombosis of the renal microvasculature, with platelet-fibrin thrombi occluding glomerular capillaries and afferent arterioles, microangiopathic hemolytic

anemia, thrombocytopenia, and decreased renal function. Similar findings have been observed when other immunosuppressives have been employed post transplantation.

Hypomagnesemia

Hypomagnesemia has been reported in some, but not all, patients exhibiting convulsions while on cyclosporine A therapy. Although magnesium-depletion studies in normal subjects suggest that hypomagnesemia is associated with neurologic disorders, multiple factors, including hypertension, high-dose methylprednisolone, hypocholesterolemia, and nephrotoxicity associated with high plasma concentrations of cyclosporine A appear to be related to the neurological manifestations of cyclosporine A toxicity.

The following reactions occurred in 3% or greater of 892 patients involved in clinical trials of kidney, heart, and liver transplants: *Renal dysfunction, hirsutism, acne, tremor, convulsions, headache, gum hyperplasia, diarrhea, nausea, hepatotoxicity abdominal discomfort, paresthesia, flushing, leukopenia, lymphoma, sinusitis, gynecomastia.*

The following reactions occurred in 2% or less of patients: *allergic reactions, anemia, anorexia, confusion, conjunctivitis, edema, fever, brittle fingernails, gastritis, hearing loss, hiccups, hyperglycemia, muscle pain, peptic ulcer, thrombocytopenia, tinnitus*

The following reactions occurred rarely: *anxiety, chest pain, constipation, depression, hair breaking, hematuria, joint pain, lethargy, mouth sores, myocardial infarction, night sweats, pancreatitis, pruritus, swallowing difficulty, tingling, upper GI bleeding, visual disturbance, weakness, weight loss.*

8.4 Labelling, Packaging, Handling and Storage of IMP and NIMP

Sites will receive labeled Eltrombopag and labeled ATGAM. There is no special handling and storage requirement for the IMP. For the NIMP, storage and shipment at 2-8 °C is required.

8.5 IMP and NIMP Accountability

Accountability for the trial IMP and NIMP at the trial site is the responsibility of the PI. The PI may delegate the responsibility of receipt, dispensing and destruction, as applicable, to the local pharmacist, or other appropriate personnel, however, this must be written in the site's delegation of authority log.

The PI will ensure that the trial drug is used only in accordance with this protocol.

Drug accountability records (logs) that are provided as part of the trials manual or sites own logs, maintained by the trial site, should indicate:

- IMP stored at site (tracking number, lot number & batch number)
- NIMP stored at site (tracking number, lot number & batch number)
- use by each patient (including IMP/NIMP name, lot number, batch number & tracking number)
- disposal of unused IMP/NIMP or destruction of used IMP/NIMP (date, lot number, batch number & tracking numbers)

8.6 Dose Modifications and Delay

8.6.1 Eltrombopag stopping rules

- Eltrombopag will be immediately discontinued at any time during the treatment in case of thrombocytosis with Plt count $>400,000/\mu\text{L}$.
- In these patients, if still prescribed as per protocol, eltrombopag will be re-introduced when Plt count $<150,000/\mu\text{L}$. Eltrombopag will be re-introduced starting with a half-dose (50 mg and 100mg from a day to another), and possibly escalated to 150 mg daily in case of Plt count remains $<150,000/\mu\text{L}$.

8.6.2 ATGAM stopping rules

- ATGAM administration will be immediately discontinued when a patient has a severe systemic reaction (e.g. anaphylactic reaction). Sign or symptoms of serum sickness or other allergic reaction should be managed without stopping ATGAM (i.e., increasing steroid dose and extending the duration of ATGAM infusion).

8.6.3 Cyclosporin A dose adjustment

The drug-drug interaction potential between eltrombopag and CsA is unknown. Both CsA and eltrombopag are inhibitors of OATP and BCRP drug transporters, and eltrombopag is a substrate of BCRP in vitro. It is not known if the combination will result in any PK changes to either drug.

Patients will be monitored for signs of CsA toxicity during the study, and therapeutic drug monitoring can be instituted as required. Cyclosporin A levels should be adjusted to maintain concentration of 200-400ng/mL (using a polyclonal assay) or 150-250 ng/mL (using a monoclonal assay). Dose may be decreased at any time in case of CsA-related adverse effects, such as hypertension, increased serum creatinine, peripheral neuropathy; dose reduction should be targeted to the higher dose effective in controlling abnormalities. In case of persisting and clinically significant abnormalities, the investigator may decide to discontinue the drug.

Rheumatoid arthritis patients with abnormal renal function, uncontrolled hypertension, or malignancies should not receive Cyclosporine A.

Psoriasis patients who are treated with Neoral should not receive concomitant PUVA or UVB therapy, methotrexate or other immunosuppressive agents, coal tar or radiation therapy. Psoriasis patients with abnormal renal function, uncontrolled hypertension, or malignancies should not receive Cyclosporine A.

Nephrotoxicity was seen early after transplantation and was characterized by a rapidly rising BUN and creatinine. Since these events are similar to rejection episodes, care must be taken to differentiate between them. This form of nephrotoxicity is usually responsive to cyclosporine A dosage reduction.

Due to the potential for additive or synergistic impairment of renal function, caution should be exercised when co-administering Cyclosporine A with other drugs that may impair renal function.

Renal and liver functions will be assessed repeatedly by measurement of serum creatinine,

serum bilirubin, and liver enzymes.

Eltrombopag dosing may be interrupted based on platelet count, reducing the potential impact of an underlying PK interaction (see paragraph 8.6.1: Eltrombopag stopping rules).

8.7 Assessment of Treatment Compliance

Will be checked by the physician in charge (see flowchart appendix 2)

8.8 Post-Trial Arrangement

Eltrombopag will only be provided to trial patients during the trial duration.

Novartis or EBMT will not provide the IMP after the protocol treatment has been completed.

Detailed work instructions will be provided on when eltrombopag and ATGAM will be delivered and how to order resupplies during the protocol duration.

8.9 Concomitant Treatment

Throughout the study the investigator may prescribe any other concomitant medications or treatments deemed necessary to manage concomitant extra-hematological diseases. Drugs potentially interfering with hematopoietic function should be avoided, if possible.

8.9.1 G-CSF

G-CSF will not be used routinely in the patients enrolled in this study; however, its use is allowed in particular clinical conditions which at judge of the investigator may take advantage of G-CSF, such as infectious complications in patients with severe neutropenia.

8.9.2 Antimicrobial and anti-fungal prophylaxis

All patients will receive antimicrobial and anti-fungal prophylaxis according to their institution's standard practice. In particular, anti-bacterial and anti-fungal agents have to be administered whenever throughout the study ANC $<0.5 \times 10^9/L$. An anti-fungal agent active on mould infections (i.e., invasive fungal infections) should be included (e.g., posaconazole or voriconazole). Prophylaxis against *Pneumocystis jirovecii* should be performed by trimetoprim-sulphamethoxazole bidaily thrice weekly, until CD4+ lymphocytes exceed 250/ μ L.

8.9.3 Anti-viral and anti-CMV prophylaxis

All patients should receive anti-viral prophylaxis by daily valganciclovir, orally. Anti-CMV prophylaxis will not be administered routinely. However, monitoring of CMV viremia and subsequent pre-emptive treatment by valganciclovir or other agents is allowed.

8.9.4 Transfusion support

Red blood cell and platelet transfusions will be given according to standard policy at investigator's discretion. As general rule, red cell transfusion should be given to maintain hemoglobin level $>8\text{gr/dL}$, or in case of clinically significant symptoms; platelet transfusions should be given when platelets $<10 \times 10^9/L$ or regardless platelet count in case of bleeding episodes. All red cell and platelet transfusions should be irradiated for life during (to prevent transfusion associated GVHD)

8.10 Excluded medications

There is no medicine for Eltrombopag and ATGAM which is prohibited per protocol in this study, provided that it is indicated according to the clinical judgement of the investigator.

Excluded medications for Cyclosporine A, due to serious drug interactions are: *St. John's Wort* (reduction in the blood concentrations of cyclosporine A), *Stiripentol* (inhibits CYP3A4 metabolism), *Bosentan* (decreases in the cyclosporine A mean dose-normalized AUC and C_{max}) and *Rosuvastatin* (Cyclosporine A causes a 7-fold increase in hepatic take up from Rosuvastatin).

8.11 Rescue medications for treatment failures

Patients who do not achieve complete or partial response at 6 months from randomisation are considered treatment failures, and will be eligible for additional treatments. Second-line treatment will be chosen at discretion of the investigator, and it will not be prescribed as per protocol. Indeed, in case of no response at 6 months a patient may exit from the study (see paragraph 6.3: early withdrawal of a patient) to receive the most appropriate second-line treatment (including bone marrow transplantation), at judge of the investigator. For these non-responder patients, bone marrow transplantation should be considered, according to established EBMT guidelines (age \leq 65 years, 10/10 HLA identical unrelated donor).

However, some patients may be eligible to receive a rescue treatment within this study (see below).

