5.2 Secondary Endpoints

1. Time to first hematological response (complete or partial) described by a cumulative incidence curve (see paragraph 9.6)
2. Time to best hematological response, described by a cumulative incidence curve (see paragraph 9.6)
3. Time to complete response (see paragraph 9.6)
4. Rates of hematological response (overall, complete, partial) at 6, 12, 18 and 24 months
5. Overall survival (OS) probability; OS is defined as time from randomisation to death, or last follow-up for patients alive
6. Event-free survival (EFS) probability; EFS is defined as time from randomisation to either relapse, death, treatment failure or clonal evolution (whichever occurs first), or last follow-up for patients alive in response
7. Cumulative incidence of relapse, from first hematological response (complete or partial) (see paragraph 9.6)
8. Cumulative incidence of clonal evolution (as defined below, see 9.5): AML, MDS or karyotypic abnormalities (see paragraph 9.6)
9. Cumulative incidence of PNH population occurrence and clinical hemolytic PNH occurrence (see paragraph 9.6)
10. Cumulative incidence of discontinuation of immunosuppressive therapy
11. Rate of CsA-independent hematological response at 24 months
12. Need for transfusions (packed red cell units and platelet units) and number of transfusions required from treatment.
13. Need for any supportive care, including hospitalization
14. Quality of life (as assessed by the validated EORTC QLQ-C30 questionnaire)(changes over time and differences between treatment arms)
15. Safety and tolerability of the investigational treatment, including SAE

6. Patient Selection and Withdrawal

All patients must meet all of the inclusion criteria and none of the exclusion criteria listed below. Protocol waivers are not acceptable in this trial.

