6.3 Early withdrawal of a patient / patient drop-out from the trial treatment

The site investigator should withdraw a patient from the trial treatment whenever continued participation is no longer in the patient's best interests. In particular, change of protocol treatment is expected in case of treatment failure (as defined in paragraph 9.4) for those patients who are eligible for second-line treatment (i.e., transplantation or second course of immunosuppression).

In addition reasons for discontinuing treatment may include:

1. the occurrence of a serious adverse event:
2. unrelated medical illness or clinical conditions representing a potential risk - at judge of the investigator, including pregnancy.
3. significant protocol violation or non-compliance (including unmotivated refusal by the subject for prescribe study procedures and post-treatment follow up).
4. a patient's own request to end treatment.

²Eltrombopag was not teratogenic when studied in pregnant rats and rabbits but caused a low incidence of cervical ribs (a fetal variation) and reduced fetal body weight at doses that were maternally toxic. There are no adequate and well-controlled studies of eltrombopag in pregnant women. The effect of eltrombopag on human pregnancy is unknown. Therefore women of childbearing potential must agree to use adequate contraception prior to (hormonal or barrier method of birth control; abstinence) and for the duration of study participation. If a woman becomes pregnant or suspects she is pregnant while on study, her treating physician should be informed immediately.

³ATGAM was not teratogenic when studied in rats or monkeys at a dose up to 20 mg/kg. However, 20 mg/kg/day ATGAM for 16 days during organogenesis in cynomolgus monkeys was fetotoxic. No fetal or maternal toxicity was seen with 10 mg/kg/day ATGAM administered for 16 days during organogenesis. There are no adequate and well-controlled studies in pregnant women. It is also not known whether ATGAM can cause fetal harm when administered to a pregnant woman or can affect reproduction capacity.

If a patient is withdrawn from treatment for any reason, he or she remains in the trial and is followed through the regular follow ups for the normal duration of the described participation as per protocol, unless the patient specifically withdraws consent from the trial.

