8.11.1 Open-label eltrombopag treatment

The following patients will be eligible for open-label eltrombopag treatment:

- Patients randomized in the control arm (ATGAM + CsA without eltrombopag) who:
 - Show no hematological response at 6 months;
 - Do not demonstrate any clonal evolution at 6 months (as confirmed by bone marrow karyotyping);

(See section 12 for related methodological issues)

All these patients are eligible to receive a course of eltrombopag; at judge of the investigator, eltrombopag will be offered as either:

- Single agent treatment;
- Eltrombopag associated with second course of immunosuppression (without any restriction concerning the anti-lymphocyte agent).

Eltrombopag treatment will be started at the same dose of 150 mg/day, and will be continued for 3 months in case of complete response at 3 months from re-introduction, or up to 6 months. After these 6 months of treatment, eltrombopag will be discontinued in any case independently from hematological response; the patients will continue the follow up, as prescribed per protocol (see paragraph 7.2).

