9.4 Definition of treatment failure

Any of following events are considered as treatment failure:

- No response at 6 months from treatment starting
- Clinical relapse
- Requirement of further (in addition to ATGAM and CyA) immunosuppressive treatment to sustain response, anytime

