9.6.5 Overall survival (OS)

Overall survival is defined as time from randomisation until death; observations will be censored for patient alive at last follow-up.

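### Section 8.11 lets 6-month non-responders leave the study although 6.3 keeps them in follow-up, and section 12 does not say how responses reached after rescue count

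*Protocol*

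**What the plan says.** - **Exit.** Protocol 8.11 treats patients without complete or partial response at 6 months as failures, leaves second-line treatment to the investigator, and says "in case of no response at 6 months a patient may exit from the study", citing 6.3.
- **Follow-up.** Section 6.3 concerns withdrawal from trial treatment and names treatment failure with second-line therapy as an expected case. Of such a patient it says "he or she remains in the trial and is followed through the regular follow ups", unless consent to the trial is withdrawn. Section 10.2.2 repeats this, and 7.2.3 sets at least 24 months of follow-up from randomisation. Withdrawal from the trial itself is in 6.4: data are collected up to withdrawal, with safety follow-up for at least 90 days after the last IMP dose.
- **Rescue inside the trial.** Section 8.11.1 offers open-label eltrombopag to "Patients randomized in the control arm (ATGAM + CsA without eltrombopag) who" have no response and no clonal evolution at 6 months, and keeps them in scheduled follow-up. It adds "See section 12 for related methodological issues". In the eltrombopag arm, re-introduction is open only to responders (8.1.1.3).
- **Analysis.** Section 12.6 applies ITT by assigned arm to all efficacy analyses. No part of section 12 mentions rescue, second-line treatment, transplant (SCT) or control-arm eltrombopag.
- **Endpoints.** Section 5.2 lists "Rates of hematological response (overall, complete, partial) at 6, 12, 18 and 24 months" and the CsA-independent response at 24 months. For OS, 9.6.5 says "observations will be censored for patient alive at last follow-up". SCT and new AA treatment are competing events for time to first, best and complete response (9.6.2 to 9.6.4). SCT is also a competing event for relapse, clonal evolution, PNH and stopping of immunosuppression (9.6.7, 9.6.8).

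**The concern.** Two separate problems follow.

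The first is missing data. A site reading 8.11 alone may close a failure's participation at month 6, and data not collected cannot be recovered by any later analysis plan. Failures are the patients most likely to die. They would also leave unevenly if control failures stay for trial-supplied eltrombopag while eltrombopag-arm failures go elsewhere. OS, clonal evolution (singled out for special attention in Appendix 5) and the late response rates would then be informatively missing.

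The second is interpretation. Even with complete follow-up, a control patient who fails ATGAM plus CsA and recovers on eltrombopag, transplant or a second immunosuppressive course counts as a control-arm responder at 12, 18 or 24 months. The protocol recognises an issue here, since it sends the reader to section 12, but nothing there addresses it.

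**Working it through.** **Scope.** The stated sample size is for 3-month CR: 7% v 21%, two-sided alpha 0.05, power 80%. The pooled two-proportion formula without continuity correction gives 96 per arm (power 80.3%), and 192/0.96 = 200. This reproduces the protocol's figures. The endpoint is read at month 3, before any exit or rescue, so it is untouched.

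**Late response rates.** Inputs from section 2: 68% response at 6 months on h-ATG, hence 32% failures; and 11 of 25 (44%) responding to eltrombopag in refractory AA. Uptake is not given and is assumed.

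Shift in control response = failures × uptake × rescue response.
- 50% uptake: 0.32 × 0.50 × 0.44 = 0.070, so 68% becomes 75%.
- 100% uptake: 0.32 × 1.00 × 0.44 = 0.141, so 68% becomes 82%.
- With an assumed 20% rescue response, uptake of 25% to 100% gives 0.016 to 0.064.

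The 44% is response in at least one lineage. PR in 9.1.2 needs transfusion independence and all three counts, so 44% is a high value for this purpose. Patients with clonal evolution at month 6 are also excluded from rescue.

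If the eltrombopag arm responds in 83% (assumed, with no rescue credited there), the difference is 83 − 68 = 15 points with rescue counted as non-response (power about 70% at 100 per arm). With rescue responses counted it is 8 points at 50% uptake (28%) and 1 point at full uptake (4%).

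**OS under literal exit.** Let p be the 6-month response and e the share of failures censored at month 6. Assumed mortality from month 6 to 24 is 2% in responders and 20% in failures; earlier deaths are ignored. Then

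KM = 1 − [0.02p + 0.20(1−p)(1−e)] / [p + (1−p)(1−e)].

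With p = 0.68 (control) and 0.88 (eltrombopag, assumed):
- No exit (6.3 followed): 92.2% v 95.8%, difference 3.6 points.
- Half exit in both arms: 94.6% v 96.9%, difference 2.3 points.
- All exit in both arms: 98.0% v 98.0%, difference 0.
- Exit in the eltrombopag arm only: 92.2% v 98.0%, difference 5.8 points.

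With 10% to 30% mortality in failures and 78% to 88% eltrombopag-arm response, the true difference is 0.8 to 5.6 points, and 0 if all failures in both arms exit. Exit shrinks the difference when even and can inflate it when one-sided. With follow-up as in 6.3 the bias is zero.

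**EFS.** Section 9.4 lists no response at 6 months, clinical relapse, and "Requirement of further (in addition to ATGAM and CyA) immunosuppressive treatment to sustain response, anytime". SCT is absent. A patient transplanted before month 6 whose counts qualify at month 6 meets none of these. The documents give no basis for a frequency.

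**The case against.** The strongest reply is that 8.11 cites 6.3, that 6.3 deals with leaving treatment rather than the trial, and that 7.2.3 requires 24 months of follow-up; read together, failures stay in and nothing is informatively censored. That is a fair reading of intent, and it limits the finding to a possible loss of data rather than a planned one. But the titles of 6.3 and 6.4 open with the same words, 8.11 quotes only that shared part, and it speaks of leaving the study. A site cannot be expected to resolve this.

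Second, section 12 is not empty: ITT by assigned arm applies to all efficacy analyses, and an SAP may add detail. This stands. ITT is a legitimate comparison of strategies that include rescue, and counting rescue as non-response is a choice of estimand. It does not fill the cross-reference, which says the content is in section 12.

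Third, the sizes rest on assumptions. That also stands. Eltrombopag-arm failures may receive transplant or second immunosuppression too and would be credited likewise, so the net shift between arms is smaller than the control shift shown.

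A reader might infer that OS and every 12- to 24-month comparison are biased. The documents do not support that. Six-month failure is already an EFS event, new AA treatment is a competing event for the time-to-response endpoints, and OS under ITT with full follow-up is valid.

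**Conclusion.** The concern holds in limited form. Sections 8.11 and 6.3 contradict each other on follow-up of failures, and the in-trial rescue option exists in one arm only. Bias in OS, clonal evolution and late response data arises only if patients actually leave. Under the assumed mortality, a true 3.6-point OS difference could read anywhere from 0 (all failures exit) to 5.8 points (exit in the eltrombopag arm only).

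The reference from 8.11.1 to section 12 leads only to the general ITT rule, so the 12-, 18- and 24-month response rates and the CsA-independent response include responses after rescue. The control rate rises by about 7 points at 50% uptake and at most 14 at full uptake, taking 44% as a high value for rescue response. Control-arm eltrombopag also blurs the clonal-evolution comparison. The EFS gap is real but probably small, since patients eligible for a sibling transplant are excluded and 8.11 places transplant after 6-month failure.

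The primary endpoint, the sample size, EFS for 6-month failures and the time-to-response endpoints are not affected. Severity: should-fix.

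**What to change.** 1. Reconcile 8.11 with 6.3 so that leaving protocol treatment for second-line therapy does not end trial follow-up to month 24, in either arm, unless consent is withdrawn. This concerns data collection only, not the choice of treatment.
2. In section 12, keep ITT by assigned arm. For the 12-, 18- and 24-month response rates and the CsA-independent response, add an analysis that counts a patient as a non-responder from the start of SCT, second immunosuppression or open-label eltrombopag. Apply the same rule for SCT and second immunosuppression to both arms, and state how eltrombopag re-introduced under 8.1.1.3 is handled; otherwise eltrombopag counts as failure in one arm only.
3. Add SCT or new AA treatment as an EFS event.
4. For clonal evolution, report ITT as the main result. An analysis that stops at control-arm eltrombopag can be a sensitivity analysis only, because it removes non-responders from one arm and is itself informatively censored.

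The cost is protocol wording and some extra tables; the visits to month 24 are already scheduled in Appendix 2. Late response rates will read lower in the added analysis.
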